6.1.2 Adverse Event Severity

The Investigator will use the following definitions to rate the severity of each adverse event:

Mild	The adverse event is transient and easily tolerated by the subject.
Moderate	The adverse event causes the subject discomfort and interrupts the subject's usual activities.
Severe	The adverse event causes considerable interference with the subject's usual activities and may be incapacitating or life-threatening.

6.1.3 Relationship to Study Drug

The Investigator will use the following definitions to assess the relationship of the adverse event to the use of study drug:

Probably Related	An adverse event has a strong temporal relationship to study drug or recurs on re-challenge and an Other cause of event is unlikely or significantly less likely.
Possibly Related	An adverse event has a strong temporal relationship to the study drug and an Other cause of event is equally or less likely compared to the potential relationship to study drug.
Probably Not Related	An adverse event has little or no temporal relationship to the study drug and/or a more likely Other cause of event exists.
Not Related	An adverse event is due to an underlying or concurrent illness or effect of another drug and is not related to the study drug (e.g., has no temporal relationship to study drug or has a much more likely Other cause of event).

For causality assessments, events meeting the categories of probably or possibly related will be considered "associated." Events that are probably not or not related will be

considered "not associated." In addition, when the Investigator has not reported a causality or deemed it not assessable, AbbVie will consider the event associated.

If an Investigator's opinion of possibly, probably not, or not related to study drug is given, an 'Other' cause of event must be provided by the Investigator for the serious adverse event.

6.1.4 Adverse Event Collection Period

[figure not shown]
All adverse events reported from the time of study drug administration until 70 days, following discontinuation of study drug administration have elapsed will be collected, whether solicited or spontaneously reported by the subject. In addition, serious adverse events will be collected from the time the subject signs the study-specific informed consent if the subject does not have the Baseline visit on the same day. Any adverse events experienced prior to first study drug administration in M11-327 will be reported in the parent protocol. Adverse event information will be collected and recorded on the appropriate eCRFs. In the event of a death, the date and reason for death should be collected.

Subjects will be contacted approximately 70 days following study drug discontinuation for an assessment of any new or ongoing AEs except those subjects who continue on adalimumab therapy after the end of study participation. These subjects are not required to complete the 70-day follow-up and any new Adverse Events should be reported through the mechanism used for all post marketing adverse experiences.

There may be instances where a 70-day follow-up phone call or clinic visit occurs after the locking of the clinical database. In this situation, any adverse events reported to AbbVie from this 70-day follow-up phone call or clinic visit will be evaluated for inclusion in the clinical database. All SAEs or Adverse Events of Special Interest, as defined by AbbVie, reported during the 70-day follow-up phone call or clinic visit must be captured in the clinical database. The 70-day follow-up phone call will not be required for any subject that initiates commercial adalimumab after the end of study participation.

Adverse event information will be collected as shown in Figure 2.

Figure 2. Adverse Event Collection

* Except for subjects who continue on adalimumab therapy after the end of study participation.

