- i. The central laboratory will perform the urine dipstick. If the urinalysis results are abnormal by dipstick, the central laboratory will perform a microscopic analysis.
- j. An annual TB test must be completed at the Week 42, 90, 138, 186, 234, 282, or 330 visits for all subjects. Please reference Section 5.3.1.1 Study Procedures for further information.
- k. If the TB test is missed at the Week 42, 90, 138, 186, 234, 282, or 330 visits, the subject must be brought in within 30 days of the visit to have the test completed.
- l. Must include a PA and lateral view. The CXR is only required if a TB test result is positive. A CXR may be repeated at any time during the study as warranted based on the opinion of the Investigator and/or CXR is inconclusive. Other diagnostic imaging tests may be performed as needed if pulmonary involvement is suspected based on the investigator's clinical assessment. See Section 5.3.1.1 for details.

Table 1. Study Activities (Continued)

- m. If a subject is enrolled in M11-327 prior to IEC/IRB approval of Global Protocol Amendment 4 of the parent study, the ANA/dsDNA sample will be collected at the subject's next scheduled visit following regulatory approval of M11-327 Global Amendment 4.
- n. If a subject develops signs and symptoms of lupus, an ANA test may be repeated based on the investigator's clinical judgment.
- o. All SAEs will be captured from the time that the subject signs the Informed Consent Form and all AEs reported from the time of study drug administration through study completion or Early Termination and at the 70-day follow up. Any adverse events experienced prior to first study drug administration in M11-327 will be reported in the parent protocol.
- p. At the Week 12 clinic visit, the subject will be dispensed two kits that include a total of four syringes. One syringe should be removed from these kits and sent back to AbbVie per the Drug Destruction guidelines. If dosing at home, the remaining three syringes from these kits will be injected at home at Weeks 12, 14 and 16. At the Week 18 clinic visit, the subject will be dispensed three kits that include a total of six syringes which should be taken at Weeks 18, 20, 22, 24, 26 and 28.
- q. Collect the packaging and any remaining drug from the last clinic visit.
- r. Subjects will have study visits every 12 weeks following Week 66 until the end of study (not to exceed 15 March 2018).

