8.1.5 Analysis of Safety

Treatment-emergent AEs will be summarized using descriptive statistics.

Treatment-emergent AEs are defined as events with an onset date on or after the first study drug administration until 70 days following the last study drug administration. In case of increasing severity of an existing AE, the worsening will be considered as a new AE with a new onset date.

AEs will be tabulated by system organ class and preferred term whereby the most current implemented MedDRA dictionary will be used. Also, summaries by severity and relationship to study drug will be done. Certain AEs, like serious or severe, leading to premature withdrawal, will be listed and described in detail. AEs of special interest for treatment with biologics will be defined in the SAP and analyzed separately.

Other safety variables like laboratory data and vital signs will be described by descriptive statistics as mentioned before. In addition, shift tables and listings will be provided for abnormal values whereby the normal range of the analyzing laboratory will be used.

The IDMC will undertake a comprehensive review and assessment of the cumulative safety data until the completion of Study M10-877 and Study M10-880. Please refer to Section 5.5.5.1 for additional information regarding IDMC review.

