Appendix D. Day 70 Follow-up (Phone Call or Clinic Visit)

Site Name/Number: _____/_____

Subject Number: _____

Please contact all subjects approximately 70 days following last study drug administration.

Date of Call/Visit: _____

- Lost to Follow-up (Please check this box if subject was not willing to provide any follow-up information or you were unable to speak to the subject following at least two phone call attempts and one certified letter).
- No Events Reported

List any Adverse Events (AE) and/or Serious Adverse Events (SAE) that occurred since the subject's last study drug administration. Please document all adverse events on a 500 AE CRF in the EDC system. (Please report all SAEs to AbbVie within 24 hours of being made aware of the event). **In addition, please note stop dates to any adverse events that were ongoing at the last study visit. If an adverse event is determined to be ongoing at the 70 day call/visit, please note in source documents and in EDC.**

_____	_____
_____	_____
_____	_____
_____	_____

Name of person completing form (printed): _____

Signature of person completing form: _____

Date: _____

Please fax this form to AbbVie at 

Subject Injection Instructions

0.8 mL dose

(Administered as a single dose-pre-filled syringe)

Protocol M11-327

Table of Contents

Dosing Schedule

General Information and Supplies

Injection Procedures

Dosing Diary Adalimumab

Instructions: To be completed for every study dose. Study medication should be taken at about the same time of day, on the same day of the week as directed by your study doctor. Please refer to the Self Injection Instructions provided to you for additional dosing information. Call the doctor's office if you are having problems administering your study medication.

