### **11.1 Treatment-Emergent Adverse Events**

Treatment-emergent adverse events (AEs) are defined as any event with an onset date that is on or after the first dose of adalimumab in Study M11-327 and no more than 70 days after the last dose of study drug administration.

If an incomplete onset date was collected for an AE, the event will be assumed to be treatment emergent unless there is other evidence that confirms that the event was not treatment emergent (e.g., the event end date was prior to the study drug start date). In case of increasing severity of an existing AE, the worsening will be considered as a new AE with a new onset date.

AE data will be summarized using primary MedDRA system organ classes (SOCs) and preferred terms (PTs) according to the most current implemented version of the MedDRA

coding dictionary. The SOCs will be presented in alphabetical order and the PTs will be presented in alphabetical order within each SOC. For AEs with an incidence rate  $\geq 5\%$  in the adalimumab group and SAEs, the PTs will also be presented in decreasing frequency.

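### The 70-day treatment-emergent window is applied to every subject, but it is not systematically collected for those who continue on non-study adalimumab, so AE counts and rates mix two observation windows

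*Protocol*

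**What the plan says.** Protocol 6.1.4 opens with a general rule: "All adverse events reported from the time of study drug administration until 70 days, following discontinuation of study drug administration have elapsed will be collected". It then provides for a contact at about day 70, "except those subjects who continue on adalimumab therapy after the end of study participation". For that group it says: "These subjects are not required to complete the 70-day follow-up and any new Adverse Events should be reported through the mechanism" that serves post-marketing experience. Later the same section adds: "The 70-day follow-up phone call will not be required for any subject that initiates commercial adalimumab after the end of study participation". The Synopsis, 5.1 and 5.4.1 repeat the exemption from contact. None of them says how soon after the study the non-study drug must start.

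Footnote o to Table 1 (Protocol 5.3.1) describes capture of "all AEs reported from the time of study drug administration through study completion or Early Termination and at the 70-day follow up". The form in Appendix D carries no exemption: "Please contact all subjects approximately 70 days following last study drug administration".

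The analysis texts carry none either. Protocol 8.1.5 counts events as treatment-emergent "until 70 days following the last study drug administration", and SAP 11.1 counts those with onset "no more than 70 days after the last dose of study drug administration". SAP 9.0 ends exposure 14 days after the last dose, and SAP 11.1 uses days of exposure as the denominator for events per 100 subject-years.

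**The concern.** Long-term safety is the primary objective, so the reader of the AE tables will take the stated window as the window observed. For subjects who go on to non-study drug, the plan schedules no AE capture after the Final visit, yet the SAP treats their next eight weeks as observed. It neither shortens the window for them nor shows how many they are.

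The excused subjects are not a random subset. Under 5.1 and 5.4.1, approval or reimbursement in a country turns the next scheduled visit into the termination visit, and the subject counts as a completer. In Japan (Appendix K, 18.0) the study concludes once approval is given. Subjects who stop early and do not go on to adalimumab keep the full 70-day contact. How long a subject is watched after the last dose therefore depends on whether adalimumab is continued and on where the subject lives.

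The protocol itself treats these late events as study data: 6.1.4 requires serious events and events of special interest reported at the 70-day contact to be entered even after database lock. Excused subjects have no equivalent contact.

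**Working it through.** The plan has no figure of its own to reproduce. Enrolment depends on rollover (Protocol 8.2) and all analyses are descriptive. The check is of the days not covered and of what they do to counts and rates.

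**Days not covered.** Dosing is every other week and no dose is given at the final visit (Protocol 5.1), so on schedule the Final visit falls about 14 days after the last dose. The visit window is ±7 days (5.3.1), giving day 7 to 21.

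- On schedule: 70 − 14 = 56 days, or 56/70 = 80% of the post-dose window.
- Range: 70 − 21 = 49 days (70%) to 70 − 7 = 63 days (90%).
- Per subject: g = 56/365.25 = 0.153 years. If all of the roughly 400 planned subjects were excused, the upper bound is 400 × 56/365.25 = 61.3 subject-years.

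**Effect on events.** Let T be mean exposure in years as SAP 9.0 defines it (to last dose + 14 days), f the share of subjects excused, and r a constant event rate. Neither f nor T is in the documents, so both are assumptions shown over a range.

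- Expected events per subject if all are followed to day 70: r(T + g).
- Expected events per subject as planned: r(T + (1 − f)g).
- Share of events lost from the stated window: f·g/(T + g).
- Reported rate relative to the true on-treatment rate (the denominator is T in every case): 1 + (1 − f)·g/T.

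| Mean exposure T | Lost, f = 25% | Lost, f = 50% | Lost, f = 100% | Rate factor, f = 0 | Rate factor, f = 50% | Rate factor, f = 100% |
|---|---|---|---|---|---|---|
| 1 year | 3.3% | 6.6% | 13.3% | 1.153 | 1.077 | 1.000 |
| 2 years | 1.8% | 3.6% | 7.1% | 1.077 | 1.038 | 1.000 |
| 4 years | 0.9% | 1.8% | 3.7% | 1.038 | 1.019 | 1.000 |

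For example, at T = 2 and f = 100%, 0.153/(2 + 0.153) = 7.1%.

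**Reading the two halves together.** Counts and percentages fall short of the SAP's own definition as f rises. The rate behaves differently. An excused subject is observed to about day 14 and contributes exposure to day 14, so numerator and denominator roughly match. A followed subject adds about 56 days of events with no exposure time. The pooled rate is therefore a blend of a matched rate and an inflated one, with weights set by how many subjects moved to non-study drug.

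**The case against.** The exemption is deliberate and is repeated in several sections. The day-70 contact serves the period after adalimumab stops, and a subject who continues on marketed drug is not in that period. Events after the switch occur on non-study product, and post-marketing reporting is a defensible route. This stands as a reason for the exemption. It does not explain why the SAP keeps an unqualified 70-day window.

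A reader might infer that late AEs and SAEs of these subjects are simply absent from the safety tables. The documents do not support that. Contact is described as not required, not as forbidden. The opening rule of 6.1.4 still covers events to day 70, solicited or spontaneous. Section 6.1.5 requires EDC entry of any serious event within 24 hours of the site learning of it, with no end date and no exception for excused subjects. What can be said is that the events are not systematically collected.

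Appendix D is a call form, and nothing shows that sites would follow it over the body text. That is fair, but the two instructions still disagree and should not.

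The sponsor could not easily recover the events by matching post-marketing cases to trial subjects, because the identification list stays at the site and is not retrieved by the sponsor (Protocol 12.1). This bears on the choice of fix.

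**Conclusion.** The point holds as a mismatch between collection and analysis. Protocol 6.1.4 and Appendix D disagree on whom to contact, and protocol 8.1.5 and SAP 11.1 state an ascertainment that 6.1.4 does not deliver for subjects who continue on non-study adalimumab. About 56 of their 70 post-dose days (49 to 63) lack systematic collection.

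The size is modest and cannot be fixed from the documents. With every subject excused, the loss is about 7% of events in the stated window at 2 years' mean exposure and about 4% at 4 years. It shrinks in proportion to the share excused and is larger for short exposure. These figures assume a constant event rate and on-schedule dosing.

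Three further inferences should be avoided:

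- **A number of missed serious events.** It would need the number excused and an event rate, and neither is given.
- **That the excused are mainly the completers.** Completers also include everyone ended by the March 2018 closure, and nothing says how many start marketed drug.
- **That the rate per 100 subject-years is understated.** Full follow-up with the present denominator would push it above the on-treatment rate.

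**What to change.** 1. Reconcile Protocol 6.1.4, Appendix D and 8.1.5 so that they agree on who is contacted and how far AE collection runs.
2. State that the site enters in the study EDC any serious event or event of special interest it becomes aware of with onset within 70 days of the last M11-327 dose, even if the event is also reported post-marketing. The site is the right party because it holds the identity list.
3. In SAP 11.1, for subjects without a 70-day contact, end the treatment-emergent window at the Final visit. List their later events separately, and report the number of subjects whose window was not observed. Using the Final visit avoids needing the date of the first non-study dose, which the documents do not provide for collecting after study exit.
4. Add one display of events per 100 subject-years in which the numerator is limited to last dose + 14 days for all subjects, the same limit as the denominator.

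Item 3 makes the main tables say what was observed but does not equalise the windows. Item 4 supplies the comparison that does not depend on who was contacted. The cost is wording changes, a few extra table rows and a small amount of site data entry. No visit, dose or treatment changes.

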6.1.5 Adverse Event Reporting

In the event of a serious adverse event, and additionally, any nonserious event of malignancy in subjects 30 years of age and younger, whether related to study drug or not, the investigator will notify Clinical Pharmacovigilance within 24 hours of the site being aware of the event by entering the serious adverse event or nonserious event of malignancy in subjects 30 years of age and younger data into the electronic data capture (EDC) system. Serious adverse events and nonserious events of malignancy in subjects 30 years of age and younger, that occur prior to the site having access to the RAVE system or if RAVE is not operable should be sent to Clinical Pharmacovigilance within 24 hours of site being made aware of the adverse event.

FAX to:		
Email:		

For serious adverse event concerns, contact the Immunology Safety Team at:

Immunology Safety Team
Immunology Development

AbbVie
[name]
[name]
USA

Fax:
Safety Hotline:
Email:

For any subject safety concerns, please contact the AbbVie Medical Monitors listed below:

For US, Canada, and Latin America:

For Europe, Israel, Australia and Japan:

Secondary Contact for Japan (Regional Medical Monitor):

██████████ and ██████████ cover for each other. For any subject safety concerns or medical emergencies in which both medical monitors are unavailable, please call the following central back-up number:

Phone: ██████████

In the EU, the sponsor will be responsible for Suspected Unexpected Serious Adverse Reactions (SUSAR) reporting for the Investigational Medicinal Product (IMP) in

accordance with Directive 2001/20/EC. The reference document used for SUSAR reporting in EU countries for adalimumab will be the most current version of the Investigator's Brochure.

6.1.6 Pregnancy

Pregnancy in a study subject must be reported to AbbVie within 1 working day of the site becoming aware of the pregnancy. Subjects who become pregnant during the study must be discontinued (Section 5.4.1). Pregnancies will be collected from the date of the first dose through 150 days following the last dose of study medication.

Information regarding a pregnancy occurrence in a study subject and the outcome of the pregnancy will be collected. Pregnancy in a study subject is not considered an AE. However, the medical outcome of an elective or spontaneous abortion, stillbirth or congenital anomaly is considered a SAE and must be reported to AbbVie within 24 hours of the site becoming aware of the event.

6.2 Product Complaint

6.2.1 Definition

A Product Complaint is any Complaint (see Section 6.0 for the definition) related to the biologic or drug component of the product or to the medical device component(s).

For a product this may include, but is not limited to, damaged/broken product or packaging, product appearance whose color/markings do not match the labeling, labeling discrepancies/inadequacies in the labeling/instructions (example: printing illegible), missing components/product, device not working properly, or packaging issues.

For medical devices, a product complaint also includes all deaths of a patient using the device, any illness, injury, or adverse event in the proximity of the device, an adverse event that could be a result of using the device, any event needing medical or surgical intervention including hospitalization while using the device and use errors.

Any information available to help in the determination of causality by the device to the events outlined directly above should be captured.

6.2.2 Reporting

Product Complaints concerning the investigational product and/or device must be reported to the Sponsor within 24 hours of the study site's knowledge of the event via the Product Complaint form. Product Complaints occurring during the study will be followed-up to a satisfactory conclusion. All follow-up information is to be reported to the Sponsor (or an authorized representative) and documented in source as required by the Sponsor. Product Complaints associated with adverse events will be reported in the study summary. All other complaints will be monitored on an ongoing basis.

Product Complaints may require return of the product with the alleged complaint condition (syringe). In instances where a return is requested, every effort should be made by the investigator to return the product within 30 days. If returns cannot be accommodated within 30 days, the site will need to provide justification and an estimated date of return.

The description of the complaint is important for AbbVie in order to enable AbbVie to investigate and determine if any corrective actions are required.

